6.3.1.2. Method of Detecting AEs and SAEs

Care will be taken not to introduce bias when detecting AEs and/or SAEs. Open-ended and non-leading verbal questioning of the subject is the preferred method to inquire about AE occurrence. Appropriate questions include:

- “How are you feeling?”
- “Have you had any (other) medical problems since your last visit/contact?”
- “Have you taken any new medicines, other than those provided in this study, since your last visit/contact?”

6.3.1.3. Follow-up of AEs and SAEs

After the initial AE/SAE report, the investigator is required to proactively follow each subject at subsequent visits/contacts. All SAEs, and non-serious AEs of special interest (as defined in Section 3.5.1) will be followed until resolution, until the condition stabilizes, until the event is otherwise explained, or until the subject is lost to follow-up (as defined in Section 4.5). Further information on follow-up procedures is given in Section 11.3.

6.3.1.4. Regulatory Reporting Requirements for SAEs

Prompt notification by the investigator to GSK of SAEs related to study treatment (even for non- interventional post-marketing studies) is essential so that legal obligations and ethical responsibilities towards the safety of subjects and the safety of a product under clinical investigation are met.

GSK has a legal responsibility to notify both the local regulatory authority and other regulatory agencies about the safety of a product under clinical investigation. GSK will comply with country specific regulatory requirements relating to safety reporting to the regulatory authority, HREC and investigators.

Investigator safety reports are prepared for suspected unexpected serious adverse reactions according to local regulatory requirements and GSK policy and are forwarded to investigators as necessary.

An investigator who receives an investigator safety report describing a SAE(s) or other specific safety information (e.g., summary or listing of SAEs) from GSK will file it with the IB and will notify the HREC, if appropriate according to local requirements.

6.3.2. Pregnancy

- Details of all pregnancies in female subjects and female partners of male subjects will be collected after the start of dosing and until after the follow-up visit.
- If a pregnancy is reported then the investigator should inform GSK within 2 weeks of learning of the pregnancy and should follow the procedures outlined in Section 11.4 (Appendix 4).

6.3.3. Physical Exams

- A complete physical examination will include, at a minimum, assessment of the Cardiovascular, Respiratory, Gastrointestinal, Dermatologic and Neurological systems, height, and weight. Height will be measured and recorded only at screening.
- A brief physical examination will include, at a minimum assessments of the skin, lungs, cardiovascular system, and abdomen (liver and spleen). Weight will be recorded with the brief physical exam as per the Time and Events Tables, but is not part of the brief physical exam.
- Investigators should pay special attention to clinical signs related to previous serious illnesses

6.3.4. Vital Signs

- Vital signs include systolic and diastolic blood pressure and pulse and will be measured in semi-supine position after 5 minutes rest.
- Temperature will also be measured as a vital sign but will not require positioning or rest prior to measuring.

6.3.5. Electrocardiogram (ECG)

- Triplicate 12-lead ECGs will be obtained for trial eligibility
- Single 12-lead ECGs will be obtained at each timepoint during the study using an ECG machine that automatically calculates the heart rate and measures PR, QRS, QT, and QTcF intervals. Refer to Section 4.5.2 for QTc withdrawal criteria.
- Withdrawal of subjects is to be based on an average QTc value of triplicate ECGs. If an ECG demonstrates a prolonged QT interval, then obtain 2 more ECGs over a brief period of time and then use the averaged QTc values of the 3 ECGs to determine whether the subject should be discontinued from the study
- Continuous cardiac telemetry will be performed. Full disclosures will be reviewed in detail and the review maintained as part of the subject's source documents

6.3.6. Clinical Safety Laboratory Assessments

All protocol required laboratory assessments, as defined in [Table 8](#), must be conducted in accordance with the Laboratory Manual, and Protocol Time and Events Schedule.

Laboratory requisition forms must be completed and samples must be clearly labelled with the subject number, protocol number, site/centre number, and visit date. Details for the preparation and shipment of samples will be provided by the laboratory and are detailed in the SRM or the laboratory manual. Reference ranges for all safety parameters will be provided to the site by the laboratory responsible for the assessments.

If additional non-protocol specified laboratory assessments are performed at the institution's local laboratory and result in a change in subject management or are considered clinically significant by the investigator (e.g., SAE or AE or dose modification) the results must be recorded in the CRF.

Refer to the SRM for appropriate processing and handling of samples to avoid duplicate and/or additional blood draws.

Hematology, clinical chemistry, urinalysis and additional parameters to be tested are listed in [Table 8](#).

Table 8 Protocol Required Safety Laboratory Assessments

Hematology			
Platelet Count	RBC Indices:		Automated WBC Differential:
RBC Count	MCV	Neutrophils	
WBC Count (absolute)	MCH	Lymphocytes	
Reticulocyte Count	MCHC	Monocytes	
Hemoglobin			Eosinophils
Hematocrit			Basophils
Clinical Chemistry (Chemistry)			
BUN	Potassium	AST (SGOT)	Total and direct bilirubin
Creatinine	Chloride	ALT (SGPT)	Uric Acid
Glucose, fasting/non-fasting*	bicarbonate	GGT	Albumin
Sodium	Calcium	Alkaline phosphatase	Total Protein
Bile Acids			
*Glucose will be fasting for all screening, day 1 pre-dose, and follow-up assessments. Glucose will be non-fasting for all other time points.			
NOTE: Details of Liver Chemistry Stopping Criteria and Follow-Up Procedures are given in Section 4.5.1 and Section 11.2 (Appendix 3)			
Routine Urinalysis (UA)			
Specific gravity			
pH, glucose, protein, blood and ketones by dipstick			
Microscopic examination (within 120 minutes of collection)			
Triglyceride Assessment (Postprandial response)			
Triglycerides			
Exploratory Pharmacodynamics (Exploratory PD Labs)			
Cholesterol			
Triglycerides			
HDL			
LDL			
VLDL-Triglycerides (if feasible)			
Other screening tests			
HIV			
Hepatitis B (HBsAg)			
Hepatitis C (Hep C antibody -- if second generation Hepatitis C antibody positive, a hepatitis C antibody Chiron RIBA immunoblot assay (or other third generation immunoassay) or Hepatitis C Virus RNA test (either quantitative or qualitative) should be reflexively performed on the same sample to confirm the result)			
FSH and estradiol (as needed in women of non-child bearing potential only)			
Serum and urine hCG Pregnancy test (as needed for women of child bearing potential)			
Urine cotinine levels			
Alcohol and drug screen (to include at minimum: amphetamines, barbiturates, cocaine, opiates, cannabinoids and benzodiazepines).			

6.4. Pharmacokinetics

Pharmacokinetic analysis will be the responsibility of the Clinical Pharmacology Modeling and Simulation Department, GlaxoSmithKline. Plasma GSK3008356 concentration-time data will be analyzed by non-compartmental methods with WinNonlin [Version 5.2 or higher]. Calculations will be based on the actual sampling times recorded during the study. Full details will be provided in the reporting and

analysis plan (RAP). The following plasma pharmacokinetic parameters will be determined for each treatment, as data permit:

Table 9 GSK3008356 Pharmacokinetic Parameters to be Estimated

Part/Day	Plasma GSK3008356 PK Parameters Calculated (as data permit)
Part 1 Single Dose	AUC(0-∞), AUC(0-t), AUC(0-24), C _{max} , t _{max} , t _{1/2}
Part 2 Day 1	AUC(0-τ), C _{max} , t _{max}
Part 2 Day 14	AUC(0-τ), C _{max} , t _{max} , t _{1/2}
Part 3 Day 1	AUC(0-τ), C _{max} , t _{max}
Part 3 Day 28	AUC(0-τ), C _{max} , t _{max} , t _{1/2}

Additional GSK3008356 PK Parameters to be Calculated:

Dose proportionality of GSK3008356 PK parameters will be assessed following single dose administration (AUC(0-t), AUC(0-∞), C_{max}) and repeat dose administration (AUC(0-τ), C_{max}).

Accumulation ratio will be determined by comparing AUC(0-τ) on Days 14 (Part 2) and 28 (Part 3) to AUC(0-τ) obtained on Day 1:

$$\text{Part 2: } R_o = [\text{AUC}(0-\tau), \text{day 14}] / [\text{AUC}(0-\tau), \text{Day 1}]$$

$$\text{Part 3: } R_o = [\text{AUC}(0-\tau), \text{day 28}] / [\text{AUC}(0-\tau), \text{Day 1}]$$

Achievement of steady-state will be determined by evaluating trough plasma concentrations (C_{trough}) following repeat oral doses, as data permit

Part 2: Plasma GSK3008356 pre-dose concentration will be determined on Days 2, 4, 5, 6, 12, 13, 14 and the 24 h post dose on Day 14 of Part 2,

Part 3: Plasma GSK3008356 pre-dose concentration will be determined on Days 2, 7, 14, 21, 28 and the 24 h post dose on Day 28 of Part 3

From the GSK3008356 urine data, the total amount excreted (A_e) will be determined following single dose in Part 1 and on Day 14 (Part 2) and Day 28 (Part 3).

Additional PK parameters may be calculated and details will be provided in the RAP. Actual elapsed times from dosing will be used in the PK analysis. Individual PK parameter values will be listed and a descriptive summary by treatment will be provided. Additional comparative plots of the PK parameters for other comparisons of interest may also be generated.

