6. STUDY ASSESSMENTS AND PROCEDURES

Protocol waivers or exemptions are not allowed with the exception of immediate safety concerns. Therefore, adherence to the study design requirements, including those specified in the Time and Events Table, are essential and required for study conduct.

This section lists the procedures and parameters of each planned study assessment. The exact timing of each assessment is listed in the Time and Events Table Section [6.1](#)

The following points must be noted:

- If assessments are scheduled for the same nominal time, THEN the assessments should occur in the following order:
 1. 12-lead ECG
 2. vital signs
 3. blood draws
 4. skin biopsy.

Note: The timing of the assessments should allow the blood draw to occur at the exact nominal time.

[figure not shown]
- The timing and number of planned study assessments, including safety, pharmacokinetic, pharmacodynamic/biomarker or others assessments may be altered during the course of the study based on newly available data (e.g., to obtain data closer to the time of peak plasma concentrations) to ensure appropriate monitoring.

- The nominal dosing time for evening dose cohorts (20:00 local) in the respective Time and Events Tables is for illustrative purposes only. The nominal evening dose time selected for use will be documented for each evening dose cohort. The actual dose time will be recorded as well.
- The change in timing or addition of time points for any planned study assessments must be documented in a Note to File which is approved by the relevant GSK study team member and then archived in the study sponsor and site study files, but this will not constitute a protocol amendment.
- The HREC and investigators will be informed of any safety issues that require alteration of the safety monitoring scheme or amendment of the Informed Consent Form.
- No more than 650 mL of blood will be collected over the duration of the study, including any extra assessments that may be required.

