6.4.2. Urine Sample Collection

Urine samples for PK analysis of GSK3008356 and for metabolite analysis will be collected at the time points indicated in the Time and Events Tables (Section 6.1). The timing of urine samples may be altered and/or samples may be obtained at additional time points to ensure thorough monitoring.

Details of urine sample collection, including volume to be collected, processing, storage and shipping procedures are provided in the SRM.

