	
Enrolled: Comprised of all subjects who consented and screened with eligibility verified.
 
Safety (Primary): Comprised of subjects who received at least one dose of study medication and had at least one safety evaluation.
 
PKC (PK Concentration) (Secondary): Comprised of subjects who received at least one dose of GSK3008356 and for whom at least one sample was obtained which yielded a valid concentration value upon bioassay.
 
PKP (PK Parameter) (Secondary): Comprised of all subjects in the PKC population who receive at least one active dose of GSK3008356 and provide pharmacokinetic parameters.
 
PD: Comprised of subjects in the Safety population for whom at least one a postprandial Triglyceride sample was obtained and analysed at baseline and post baseline.

Hypothesis	There are no formal hypotheses being tested.
Primary Analyses	Safety data will be presented either in tabular and/or graphical format and summarised descriptively. GSK's Integrated Data Standards Library (IDSL) standards for the displays are being used
Secondary Analyses	
Pharmacokinetic:
 
 
• Summary Statistics for AUC(0-∞) on Day 1, AUC0-Tr, Cmax, Tmax on Day 1 and Day 14, and t1/2, Ae, and CLr on Day 14 of GSK3008356 as data permit.
 
 
Dose Proportionality:
 
 
• Assessment of dose proportionality by AUC(0-∞) on Day 1, AUC0-tau and Cmax on Day 1 and Day 14;
 
 
Accumulation Ratio:
 
 
• Assessment of observed accumulation ratio by AUC(0-tau), (Ro), and Cmax (Rcmax) on Day 14 vs. Day 1 as data permit.
 
• Assessment of steady-state accumulation ratio (Rs) by AUC(0-tau) on Day 14 vs. AUC(0-∞) on Day 1 as data permit.
 
 
Steady State:
 
 
• Assessment of steady state after repeat dosing by trough plasma concentration on Days 2, 4, 5, 6, 12, 13, 14 (pre-dose), 15 (24 h post-dose on Day 14).
 
 
Pharmacodynamic (TG):
 
 
• Summary statistics for absolute for TG values by treatment and day and time point
 

Overview	Key Elements of the RAP

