
Part 2 14d Repeat Dose
 
To determine the pharmacokinetics of GSK3008356 after 14 daily doses in healthy subjects;
 
To assess dose proportionality of GSK3008356 after 14 daily doses in healthy subjects;
 
To examine the extent of accumulation and achievement of steady-state following 14 daily doses of GSK3008356 in healthy subjects;
 
To evaluate the preliminary pharmacodynamics after 14 daily repeat doses of GSK3008356 in healthy subjects.
	
Part 2 14d Repeat Dose
 
PK endpoints include the AUC(0-∞) on Day 1, AUC(0-τ), Cmax, and tmax on Day 1 and 14, and t1/2, Ae, and CLr on Day 14 of GSK3008356 as data permit;
 
AUC(0-∞) in Day 1, AUC(0-τ) and Cmax on Day 1 and 14 for the assessment of dose proportionality as data permit;
 
Observed accumulation ratio based on AUC(0-τ), (Ro), and Cmax (RCmax) on Day 14 versus Day 1 as data permit. The steady-state accumulation ratio (Rs) by AUC(0-tau) on Day 14 vs. AUC(0-∞) on Day 1 as data permit.
 
Trough plasma concentrations (Ctrough) to assess steady state after repeat dosing, as data permit;
 
Fat challenge meal postprandial triglyceride levels.

Exploratory	

Part 2 14d Repeat Dose
 
To evaluate the change in serum lipid levels and weight after 14 daily repeat doses of GSK3008356 in healthy subjects
 
To evaluate the impact of evening dosing on tolerability.
 
To evaluate partitioning of GSK3008356 into skin.
	
Part 2 14d Repeat Dose
 
Serum Lipid panel, weight;
 
Clinical monitoring/observation for adverse events with a focus on gastrointestinal findings and a stool scale.
 
Skin biopsy for drug concentration and activity.

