**Table 7 Derived Pharmacokinetic Parameters**

Parameter	Parameter Description
AUC (0-t) (Part 1)	Area under the concentration-time curve from time zero to the time of the last quantifiable concentration (C(t)) will be calculated using the linear trapezoidal rule for each incremental trapezoid and the log trapezoidal rule for each decremental trapezoid.
AUC (0-τ) (Part 2)	Area under the concentration-time curve from time zero to the time of the end of dosing interval (C(T)) will be calculated using the linear trapezoidal rule for each incremental trapezoid and the log trapezoidal rule for each decremental trapezoid.
AUC (0-24) (Part 1)	Area under the concentration-time curve from time zero to the time of the 24 hour concentration (C(24h)) will be calculated using the linear trapezoidal rule for each incremental trapezoid and the log trapezoidal rule for each decremental trapezoid.
AUC 0-∞ (Part 1 + Part 2 day 1)	Area under the concentration-time curve extrapolated to infinity will be calculated as: AUC(0-inf) = AUC(0-t) + C(t) / lambdaz This parameter will only be calculated for the single-dose profiles in Part 1 and Day 1 in Part 2.
C max	Maximum observed concentration, determined directly from the concentration-time data.
C t	Last quantified observed concentration, determined directly from the concentration-time data.
T max	Time to reach C max , determined directly from the concentration-time data.
t 1/2	Apparent terminal half-life will be calculated as: t1/2 = ln2 / lambdaz
A e	Cumulative amount of drug excreted in urine. $A_e = \sum C_{ur} * V_{ur}$ Where C ur is the concentration in urine and V ur is the volume of urine
CL r	Renal Clearance [1] Single Dose: CL r = A e /AUC inf [2] Repeat Dose: CL r = A e τ /AUC τ Where A e τ is cumulative amount of drug excreted in urine over a dosing interval.
C trough (Part 2)	Observed Concentration at the end of a dosing interval, immediately before next administration. Directly obtained from the observed concentration vs. time curves. They are the pre-dose concentration on Days 2, 4, 5, 6, 12, 13, 14 and the 24 h post dose on Day 14.

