## 11.12.5.4. Pharmacokinetic Tables

Pharmacokinetic: Tables					
No.	Population	IDSL / TST ID/ Example Shell	Title	Programming Notes (U)nique/(R)epeat	Deliverable
Concentration-time					
4.1 4.2	PKC	PK01	Summary of Plasma Pharmacokinetic Concentration-Time Data by Treatment (Part X)	IDSL (U)	SAC
4.3	PKC	PK01	Summary of Pharmacokinetic Trough Plasma Concentration-Time Data by Treatment (Part 2)	IDSL (R)	SAC
Pharmacokinetic Parameters: Analyses					

Pharmacokinetic: Tables					
No.	Population	IDSL / TST ID/ Example Shell	Title	Programming Notes (U)nique/(R)epeat	Deliverable
4.4 4.5	PKP	PK03	Summary of Derived Pharmacokinetic [units] by Treatment (Part X)	IDSL (U) All derived PK parameters were listed in Table 6 in the section. They are as follows: Part 1: AUC(0-t), AUC(0-24), AUC(0-inf). Part 2: AUC(0-tau), Ro and R max , R s , C trough . Part 1 + Part 2 on Day 1: AUC(0-inf) Part 1 + Part 2: C max on Day 1 in part 1 and Days 1, 14 in part 2. T max , t 1/2 , A e , CL r on . on Day 1 in part 1 and Day 14 in part 2	SAC
4.6 4.7	PKP	PK03	Summary of Log-Transformed Derived Pharmacokinetic [units] by Treatment (Part X)	IDSL (U) All Log-Transformed derived PK parameters were listed in Table 6.	SAC
4.8 4.9	PKP	Non-standard Mock PK_T1	Summary of Statistical Analysis of Dose Proportionality (Part X)	(U) Please follow the sample code in the Section 8.1.3.2: Statistical Analysis of Pharmacokinetic Parameters.	SAC
4.10	PKP	Non-standard Mock PK_T2	Summary of Statistical Analysis of Accumulation Ratio (Part 2)	(U) For R o , R max Please follow the sample code in the Section 8.1.3.2: Statistical Analysis of Pharmacokinetic Parameters	SAC
4.11	PKP	Non-standard Mock PK_T3	Summary of Statistical Analysis of Assessment of Steady-State (Part 2)	(U) Please follow the sample code in the Section 8.1.3.2: Statistical Analysis of Pharmacokinetic Parameters	SAC

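### Minor inconsistency: Part 2 keeps Day 14 Ae and CLr as secondary endpoints although no Part 2 table schedules urine PK, and the Part 1 CLr formula mismatches intervals for Cohort 8

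*Protocol*

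**What the plan says.** **Endpoints.** Protocol Section 2 lists Ae and CLr on Day 14 among the Part 2 secondary PK endpoints. Protocol 6.4 says that Ae from the urine data "will be determined following single dose in Part 1 and on Day 14 (Part 2) and Day 28 (Part 3". The SAP repeats this in its synopsis ("on Day 14 of GSK3008356 as data permit") and in 2.3 ("t1/2, Ae, and CLr on Day 14 of GSK3008356 as data permit"). SAP Table 6 carries Ae and CLr for both parts. Table 7 gives a repeat-dose CLr of Ae over tau divided by AUC over tau, where the numerator "is cumulative amount of drug excreted in urine over a dosing interval". The programming note for displays 4.4 and 4.5 calls for Ae and CLr "on Day 1 in part 1 and Day 14 in part 2".

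**Collection.** Under Protocol 6.4.2, urine samples for PK "will be collected at the time points indicated in the Time and Events Tables". The Part 1 table (Protocol 6.1.1, repeated in SAP 11.2.1.1) has a urine PK row, with a pre-dose sample and post-dose intervals of 0-12 h and 12-24 h.

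**Part 1 formula.** SAP Table 7 defines single-dose CLr as Ae divided by AUC to infinity. The same table derives AUC(0-24) for Part 1 and AUC(0-tau) for Part 2 only.

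**The concern.** The endpoint list and the schedule do not agree. Two named Part 2 secondary endpoints need drug concentration and volume in urine collected over a dosing interval, and nothing in the Part 2 schedule provides that. The SAP restates the endpoints and reproduces the schedule without reconciling them, although it records openly that Part 3 and the PK/PD modelling will not be done. A reader who meets empty Day 14 cells could not tell whether urine was never scheduled, was collected but not assayable, or was lost because subjects stopped early.

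The second issue is whether the numerator and denominator of CLr cover the same time. In Part 1 the urine stops at 24 h and the plasma AUC is extrapolated to infinity. That hardly matters when all the drug is given early in the day. It matters more for a regimen whose second dose falls 8 h before urine collection ends.

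**Working it through.** **1. Endpoint against schedule.** Rows for timed urine PK collection:

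| Tables | Urine PK row |
|---|---|
| Part 1: Protocol 6.1.1; SAP 11.2.1.1 | present in both |
| Part 2 main tables: Protocol 6.1.2 to 6.1.7 | 0 of 6 |
| Part 2 meal/PK tables: Protocol 6.1.8.1, 6.1.8.2 | 0 of 2 |
| Part 2 main tables: SAP 11.2.1.3 to 11.2.1.5 | 0 of 3 |
| Part 2 meal/PK table: SAP 11.2.1.6 | 0 of 1 |

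A row lost in reading the PDF is unlikely. It survives in both Part 1 copies, and the Day 14 metabolite footnotes (Protocol 6.1.4, SAP 11.2.1.5) mention plasma only, where the Part 1 footnote describes urine as well. The SAP's Part 2 tables are not a straight copy either: they show skin biopsy on Days 1 and 2, which the protocol's tables do not, yet still no urine PK. The other Part 2 urine tests are the urinalysis in Protocol Table 8 (dipstick and microscopy), the drug and cotinine screen and the hCG test. None gives a timed volume and a drug concentration, so none supplies the numerator.

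**2. Who could contribute on Day 14.** Planned active subjects: 3 cohorts x 6 = 18. SAP 2.2 says dosing in Cohort 1 stopped for everyone before Day 7: 18 - 6 = 12. One subject in Cohorts 2 and 3 did not complete, with treatment not stated: 11 or 12. This assumes full enrolment and no replacements.

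**3. Part 1 CLr.** Take equal doses, linear kinetics, constant CLr and exact AUCs. Then

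Ae(0-24)/AUCinf = CLr x (1 - f),

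where f is the share of AUCinf lying after 24 h. It is the average, over doses given at time d, of tail(24 - d). With instantaneous absorption and half-life h, tail(T) = 2^(-T/h). The observed h is 1.5 to 3 h (Protocol 3.1.1). Cohort 8 dose times are in SAP 8.2.1.1 and 11.5.1.

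Cohort 8 (0 h, 16 h):
- h = 1.5: 0.5 x (2^(-16) + 2^(-5.33)) = 0.5 x (0.00002 + 0.0248) = 1.24%
- h = 3: 0.5 x (2^(-8) + 2^(-2.67)) = 0.5 x (0.0039 + 0.1575) = 8.07%

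| Regimen | h = 1.5 h | h = 3 h |
|---|---|---|
| Single dose at 0 h | 0.002% | 0.39% |
| Cohort 7 (0 h, 4 h) | 0.006% | 0.69% |
| Cohorts 10 and 11 (hourly, 0 to 8 h) | 0.018% | 1.17% |
| Cohort 8 (0 h, 16 h) | 1.24% | 8.07% |

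As a sensitivity check, use a one-compartment model with an assumed ka of 1.4/h and tail(T) = (ka e^(-ke T) - ke e^(-ka T))/(ka - ke). Cohort 8 becomes 1.85% to 9.67%, and every other regimen stays at 1.40% or less. The pattern does not depend on instantaneous absorption.

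**The case against.** Protocol 6.4 states the intention to determine Day 14 Ae, so it is the collection times that are missing, not the intent. The protocol also leaves room to supply them. Section 6.4.2 says that "samples may be obtained at additional time points to ensure thorough monitoring" and places collection details in a Study Reference Manual that is not among the documents. Section 6 says that an added time point "must be documented in a Note to File which is approved by the relevant GSK study team member" and does not need an amendment. The endpoints are qualified by data availability and the urine assay by feasibility. Ae and CLr receive descriptive statistics only, enter none of the dose-proportionality, accumulation or steady-state models, and are not in the minimum data set for escalation in Protocol 9.8.1. All of this stands, and it makes the point minor. None of these provisions schedules a Day 14 collection, however.

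A reader might infer that Day 14 urine was never taken, or that endpoint data were lost. The documents do not support that. They show a gap in the schedule and are silent on whether samples were added.

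On Part 1, it is fair to say that Table 7 labels the AUCinf formula as single-dose, that the SAP codes Cohort 8 as multiple-dose, and that no sentence assigns a CLr formula to that cohort. But the repeat-dose formula needs AUC over tau, which Table 7 derives for Part 2 only, whereas SAP 8.1.3.2 plans AUCinf for the Part 1 multiple-dose regimens. Ae/AUCinf is therefore the only CLr formula whose denominator the SAP derives for Cohort 8. A reader might take this as a fault in Part 1 CLr generally. The figures do not support that: for true single doses the effect is below 0.4%.

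**Conclusion.** The plan has a minor internal inconsistency. Day 14 Ae and CLr are Part 2 secondary endpoints with planned displays, but the schedule in either document gives them no urine data. At most 11 or 12 active subjects reached Day 14, on the assumptions stated. The table comparison is certain; whether urine exists is unknown.

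The Part 1 formula is a separate, small bias confined in practice to Cohort 8 (6 active subjects), where CLr would be understated by about 1% to 8%. That range rests on the observed 1.5 to 3 h half-lives, instantaneous absorption, linear kinetics and use of the AUCinf formula. It isolates the interval mismatch and no other source of error in the AUC. No model or decision in the plan rests on either result.

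Part 3 shows the same absence of urine PK rows against its Day 28 endpoints, but it was not initiated, so nothing follows for the analysis.

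**What to change.** 1. Check the site records and Notes to File for any Day 14 urine PK collection in Part 2.
2. If there was none, restrict Ae and CLr to Part 1 in the SAP synopsis, 2.3, Tables 6 and 7 and displays 4.4 and 4.5. State in SAP 2.1 that the Part 2 values are not evaluable because collection was not scheduled.
3. If there was some, state the collection intervals in the SAP and keep Ae over tau divided by AUC over tau.
4. In either case, define Part 1 CLr in Table 7 as Ae(0-24)/AUC(0-24). The AUC is already derived, both quantities then cover the same 24 h, and one rule serves single-dose and multiple-dose cohorts.

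The cost is one check of existing records and some SAP wording. No new samples, subjects or visits are needed.
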